9.5 Data sources

The National Prostate Cancer Register (NPCR) of Sweden captures 98% of all newly diagnosed prostate cancer cases since 1998 (8). By use of the unique Swedish Person Identity Number (PIN), the NPCR has been linked with a number of other health care registries to create PCBaSe. These include the National Cancer Registry, the National Patient Registry (with hospital and outpatient hospital clinic diagnoses), the Cause of Death Registry, the Prescribed Drug Registry with dispensed prescriptions since July 2005, and the Swedish longitudinal integration database for health insurance and labour market studies (LISA), which is a socioeconomic database with information on the educational level, income, and marital status of patients (8).

PCBaSe contains more than 180,000 Pca cases diagnosed between 1998 to 2016. The linkage of registries means PCBaSe contains comprehensive data on tumour characteristics, patients demographic, clinical and socioeconomic characteristics as well as treatment delivered or decided upon up to six months after date of diagnosis. In addition, there over 900,000 Pca-free control men (five for each PCa case matched on birth year and county of residence) derived from the general population of men in Sweden.

From PCBaSe, it is possible to extract data on the patients' dispensed drug prescriptions for anticoagulants and partially for anti-cancer therapies (since July 2005 when the Prescribed Drug Registry started). We are also able to use the in- and outpatients registries to detect any diagnosis of VTE events experienced by the patients (defined as pulmonary embolism or deep vein thrombosis). The ATC codes for the anticoagulant and anti-cancer drugs, as well as the ICD-10 codes for the VTE diagnosis are described in annex 3.

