9.3.3 Outcomes of interest

In men with PCa:

1. DVT or PE
2. Bleeding events leading to hospitalisation
3. Mortality

In PCa-free men:

4. DVT or PE

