9.4 Follow up

9.4.1 Exposure to anticoagulants

The exposure to AC treatment will be defined in two ways:

- the first is by following the patients until the end of the follow-up time, regardless if they are still on the drug or not.
- the second way is to follow up the patients until the filled prescription for each respective drug expires (“on/treatment”).

A grace period of 90 days will be used to define a new prescription of anticoagulant. The duration of a prescription will be derived from the median number of days between consecutive respective prescriptions after the grace period has passed.

The treatment exposure can then be used to study the switching of treatments and the discontinuation of treatments.

A start date will be defined as the date of the dispensed prescription for patients receiving anticoagulation.

Patients will be censored at earliest date of:

- Time of first occurrence of a recurrent VTE event or a bleeding event (major bleeding event i.e. intracranial, gastrointestinal, urogenital bleeding, or other bleeding leading to hospitalisation) or death
 - Patients will be followed until occurrence of one of the above mentioned outcomes of interest; similarly, the analysis is repeated in the same way for the other outcomes of interest. Therefore, the patients were not censored at the first outcome of interest and outcomes on treatment after the first is also taken in to account. Only first-time events of the same type are considered.
- End of observation time (data lock point for the database at 31st October 2017)
- Treatment discontinuation
- Treatment switching patients who switched will be censored at the time of the date of a filled prescription from a pharmacy of the new drug.

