9.8 Data analysis

Descriptive statistics will be used to define the socio-demographic and clinical characteristics (including main types of cancer therapies) of all PCa patients at the time of PCa diagnosis (Objective 1 and 3) and PCa-free men at the time of inclusion in PCBaSe (Objective 8) and include variables of interest listed above.

All categorical variables will presented by counts and proportions and continuous variables by mean, standard deviation, range, median, and first and third quartiles.

The occurrence will be estimated by calculating an incidence rate (accompanied by 95% CI) of cancer-related VTE events, split into PE and DVT events, in men with PCa (Objective 2) and in PCa-free men (Objective 10). The incidence rate is defined as the number of events of interest divided by the total number of person-years at risk. In men with PCa, the person-time at risk will be calculated from date of incident PCa diagnosis up until an outcome of interest, death or end of follow-up, whichever came first. The occurrence will be also described by Kaplan-Meier curves in different strata within different time-periods.

The AC treatment received by the PCa patients after a first cancer-related VTE event on an out-patient long-term basis will be reported by type of anticoagulation (LMWH, VKAs and NOACs) and its estimated duration (from the time-point of a hospital discharge up to 3 months, 3-6 months, more than 6 months) (Objective 4).

Time at risk for Objectives 5, 6 and 7 (recurrent VTE, bleeding leading to hospitalisation or death) will be calculated from first cancer-related VTE (the time-frame of defining cancer-relatedness will be specified later) for each events of interest up until event, death or end of follow-up.

The 95% CI for the incidence rate will be calculated using the Poisson distribution.

Incidence rates of recurrent VTE, bleedings and death will be calculated by the type and duration of AC treatment (stratification variables); however no comparative analysis of outcomes in three sub-groups of AC treatments, is planned.

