Annex 3: Additional information

Table 1. ATC codes for anticoagulant drugs

Class	Drug name	ATC code
1. Parenteral anticoagulants	Heparin	B01AB01
	Enoxaparin	B01AB05
	Dalteparin	B01AB04
	Nadroparin	B01AB06
	Tinzaparin	B01AB10
	Reviparin	B01AB08
	Parnaparin	B01AB07
	Bemiparin	B01AB12
	Fondaparinux	B01AX05
	Danaparoid	B01AB09
	Bivalirudin	B01AE06
	Argatroban	B01AE03
	2. Vitamin K antagonists	Warfarin
Phenprocoumon		B01AA04
Acenocoumarol		B01AA07
Dicoumarol		B01AA01
Tioclomarol		B01AA11
Ethyl biscoumacetate		B01AA08
Fluindione		B01AA12
Phenindione		B01AA02
Chlorindione		B01AA09
Diphenadione		B01AA10
3. Non-vitamin K oral anticoagulants (NOACs)	Rivaroxaban (Xarelto)	B01AF01
	Dabigatran (Pradaxa)	B01AE07
	Apixaban (Eliquis)	B01AF02
	Edoxaban (Savaysa/Lixiana)	B01AF03

Tabel 2. ICD-10 codes used to define disease conditions

Condition	ICD-10 or Swedish procedure code beginning with
Intracranial bleeding	I60-62, S064, S065, S066
Gastrointestinal bleeding	I850, I983, K226, K250, K252, K254, K256, K260, K262, K264, K266, K270, K272, K274, K276, K280, K284, K286, K290, K625, K661, K920, K921, K922
Urogenital bleeding	N02, R319, N95
Other bleeding	H431, R04, R58, D629, procedure code DR029
Anaemia	D50-64
Coagulation or platelet defect	D65-69
Ischaemic stroke	I63
Heart failure	I50, I110, I130, I132, I255, K761, I42-43
Unspecified stroke	I64
TIA	G45
Peripheral systemic emboli	I74
Thromboembolism (composite)	I63-64, G45, I74
Pulmonary embolism	I26
Deep venous thrombosis	I801-802
Venous thromboembolism (composite)	I26, I801-802
Myocardial infarction	I21, I252
Ischaemic heart disease	I20-25

“Swedish alcohol index” : will be used with ICD-10 codes: E244, F10, G312, G621, G721, I426, K292, K70, K860, O354, P043, Q860, T51, Y90-91, Z502, Z71

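### VTE is to be found in hospital registers only, so a PE that is fatal without a hospital diagnosis counts as a death without VTE; the linked Cause of Death Registry would allow a cheap with-and-without check

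*Protocol*

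**What the plan says.** Objective numbers follow the list in the abstract. Section 9.8 labels VTE in PCa-free men Objective 10, where the abstract has 9.

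- **Source for VTE.** Section 9.5 says "We are also able to use the in- and outpatients registries to detect any diagnosis of VTE events experienced by the patients". No other source for VTE is named in the protocol.
- **Linked registers.** The same section lists "the National Patient Registry (with hospital and outpatient hospital clinic diagnoses), the Cause of Death Registry" among the registers that make up PCBaSe. Causes of death are therefore in the research database already.
- **Codes.** Annex 3 gives "Venous thromboembolism (composite) I26, I801-802". It has no rule on whether these codes count when they appear as a cause of death.
- **Time at risk.** For first VTE in men with PCa, section 9.8 runs person-time "up until an outcome of interest, death or end of follow-up, whichever came first". For recurrent VTE, bleeding and death it is counted "for each events of interest up until event, death or end of follow-up".
- **Other outcomes.** Section 9.3.3 lists "Bleeding events leading to hospitalisation" and, separately, mortality without a split by cause.
- **Limitations.** Section 9.10 discusses in-hospital drugs, missing lifestyle data and adherence. It does not mention outcomes that never reach hospital.

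**The concern.** A man who dies of a PE at home, with no hospital or hospital-clinic diagnosis of it, has no VTE under the source named in section 9.5. His person-time ends at death and he appears only in mortality. The occurrence of VTE is a main quantity of the study (Objective 2 in men with PCa, Objective 9 in PCa-free men), and recurrence (Objective 5) is affected in the same way. Section 7 itself presents VTE as a major cause of death in cancer, so fatal events are part of what the study sets out to describe.

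This mechanism works in one direction only: it removes events and adds none. The cohort is also large enough that the confidence intervals will be very narrow, and they will not reflect this kind of error.

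**Working it through.** **1. The protocol's precision table (section 9.6).** With N = 98 000 and p = 4 900/98 000 = 5%, the 95% half-width is h = 1.96 × √(p(1 − p)/N) = 1.96 × √(0.05 × 0.95/98 000) = 0.136 points. The full width is 0.273; the table has 0.28, the difference of its rounded limits 4.86 and 5.14. At p = 1%, h = 0.062 and the width is 0.125 (table: 0.12). The table's widths reproduce to within 0.01 point, so there is no error of calculation here.

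**2. Effect of missed fatal events.** Let f be the share of all VTE events that are fatal and have no hospital record. The documents give no value, so **f is an assumption**, shown over 1% to 15%. If x events are recorded:

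- all events = x/(1 − f)
- missed events = x·f/(1 − f)

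For first VTE the person-time does not change, because a register-only event is dated at death, where follow-up stops anyway. The recorded rate is therefore (1 − f) times the full rate.

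| Assumed f | 4 900 recorded (5.00%): missed | Full incidence | 980 recorded (1.00%): missed | Full incidence |
|---|---|---|---|---|
| 1% | 49 | 5.05% | 10 | 1.01% |
| 3% | 152 | 5.15% | 30 | 1.03% |
| 5% | 258 | 5.26% | 52 | 1.05% |
| 10% | 544 | 5.56% | 109 | 1.11% |
| 15% | 865 | 5.88% | 173 | 1.18% |

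For example, 4 900/0.95 = 5 158 and 5 158/98 000 = 5.26%; 980/0.95 = 1 032 and 1 032/98 000 = 1.05%.

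**3. Comparison with sampling error.** The shift p·f/(1 − f) equals the half-width h when f = h/(p + h):

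- at 5% recorded: 0.136/5.136, about 2.7%
- at 1% recorded: 0.062/1.062, about 5.9%

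At f = 5%, then, the shift exceeds the half-width in the 5% row (0.26 against 0.14 points). In the 1% row it stays inside the stated interval of 0.94 to 1.06.

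**4. PCa against PCa-free men.** The ratio of the two recorded rates is multiplied by (1 − f₁)/(1 − f₀), where f₁ applies to men with PCa and f₀ to PCa-free men. Equal shares leave the ratio unchanged. An assumed 10% against 5% gives 0.90/0.95 = 0.947, and 5% against 10% gives 0.95/0.90 = 1.056. The documents do not say whether the shares differ. Section 9.8 also does not spell out when person-time ends for PCa-free men; I assume the same rule.

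**The case against.** **The source is not stated to be exclusive.** Section 9.5 describes what the team is able to use, and nothing rules out the Cause of Death Registry. Which registers and diagnosis positions define a case is often settled in an analysis plan, which is not at hand. This stands in part: exclusivity is my inference. But the protocol does name a source for VTE, names only one, and gives no rule for cause-of-death codes.

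**Fatal events are not all lost.** A reader might infer that the plan drops fatal VTE altogether. It does not. A fatal PE diagnosed in hospital is in the Patient Registry and counts; only deaths with no hospital diagnosis of the event are missed. All deaths enter total mortality.

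**Bleeding.** A reader might infer that Objective 7 is biased downward because fatal bleeds at home are not counted. The documents do not support that. Hospitalised bleeding is the declared outcome, and a bleed outside hospital lies outside it. The censoring rule in section 9.4.1, "major bleeding event i.e. intracranial, gastrointestinal, urogenital bleeding, or other bleeding leading to hospitalisation", may even attach hospitalisation to other bleeding only, but it adds no death-register source. Widening the outcome, or splitting mortality by cause, would be a change of scope.

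**Size.** No figure in the protocol supports any f, and the 5% row is a favourable example. The protocol itself places PCa among the cancers with relatively low VTE risk. This stands.

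**Death-register codes bring problems of their own.** They are less specific than hospital diagnoses. After an index PE, the same code on a death certificate may refer to the index event. A man whose first VTE is his death has no follow-up and no chance of an outpatient dispensing. All of this stands and shapes the fix.

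**Conclusion.** The point holds for VTE, as a cheap improvement and not as the correction of an error. As the protocol is written, a PE that is fatal without a hospital diagnosis is a death without VTE. Through this mechanism the rates for Objectives 2, 5 and 9 can only be too low, by a factor (1 − f).

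The conclusion rests on reading the one source named in section 9.5 as the only one. Its size rests wholly on an assumed f. At 5%, the effect is 0.26 points on a recorded 5.00% and 0.05 points on a recorded 1.00%. It may therefore exceed the sampling error or stay within it, and the documents cannot settle which. They also do not show that the missed share differs between PCa and PCa-free men; section 9.2.4 says both have the same information sources. For bleeding, the gap is a limitation to disclose.

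**What to change.** 1. **Objectives 2 and 9.** In sections 9.5 and 9.8 and Annex 3, keep the hospital-only VTE rates. Report beside them rates that add deaths with I26 or I801-802 as underlying cause and no earlier hospital VTE record, dated at death. Show contributory cause as a further variant. Apply the same rule to PCa and PCa-free men.
2. **VTE sub-population.** State that men whose first VTE is known only from the death register and was fatal do not enter the sub-population for Objectives 4 to 7.
3. **Objective 5.** Add death-register VTE as a sensitivity analysis only. Use underlying cause and a stated minimum interval after the index event, so that the index event is not counted as its own recurrence.
4. **Section 9.10.** List fatal VTE and fatal bleeding without hospital contact as a limitation. A sensitivity analysis adding deaths with a listed bleeding code as underlying cause is optional.

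The cost is some protocol wording, a few lines of code and an extra set of table columns, since the register is already linked. The drawback is the lower specificity of cause-of-death coding, which is why both versions should be shown and neither should replace the other.

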9.2.3 Selection criteria from PCBaSe

PCa patients

Inclusion criteria

Initially all patients newly diagnosed with PCa between 2007-2016 with at least one year before the end of follow up date (31 December 2017) will be included.

From this population, a sub-population of PCa patients with a first cancer-related VTE event will be selected.

Exclusion criteria

No exclusions will be made.

Men without PCa

Inclusion criteria

All PCa-free men included in PCBaSe who are randomly selected from the general population of Sweden with the same birth year and county of residence of PCa patients diagnosed between 2007-2016.

Exclusion criteria

A PC free men diagnosed with a prostate cancer during the follow up will be identified and censored.

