9.3 Variables

Baseline is defined as:

- in men with PCa: a date of an incident PCa
- in PCa-free men: a date of selection of PCa-free men (who are alive) into the database corresponding to the date of diagnosis for the index case

Index date is defined as:

- in men with PCa:
 - a date of a first cancer-related VTE event that is a VTE event related to the diagnosis of PCa (to define the relatedness, different time-frames will be specified and applied);
- in PCa-free men:
 - a date of selection into the database for defining a first recorded VTE event.

9.3.1 Characteristics of PCa and (where possible) PCa-free men:

- Age at PCa diagnosis
- Age at VTE
- Charlson Comorbidity Index (CCI) based on discharge diagnosis (including variables included into CCI)
- Specific events at baseline (that occurred prior and at the baseline) define by ICD codes for:
 - intracranial bleeding
 - gastrointestinal bleeding
 - urogenital bleeding
 - ischaemic heart disease
 - myocardial infarction

- heart failure
- stroke (ischaemic and haemorrhagic)
- transient ischaemic attack
- atrial fibrillation
- renal impairment
- renal failure
- depression
- hypertension
- hyperlipidaemia
- diabetes
- asthma
- COPD
- other cancers than PCa
- previous VTE events
- Co-medications at baseline (120 before the index event) and during follow-up (from index date)
 - Antiplatelets
 - Proton pump inhibitors
 - NSAIDs
 - SSRIs
 - Oral steroids
 - Antibiotics
 - Lipid-lowering medications
- PCa/specific parameters:
 - County
 - Hospital type (university, non-university)
 - Clinical TNM staging
 - PSA (at time of PCa diagnosis)
 - PCa risk categories (defined at diagnosis according to a modification of the National Comprehensive Cancer Network Guideline):
 - a. Low-risk: T1-2, Gleason score of 2–6 and PSA < 10 n/ml
 - b. Intermediate-risk: T1-2, Gleason score 7 and/or PSA 10–20 ng/ml
 - c. High-risk: T3 and/or Gleason score 8–10 and/or PSA 20–50 ng/ml

- d. Regionally metastatic T4 and/or N1 and/or PSA 50–100 ng/ml
 - e. Distant Metastatic disease: or M1 and/or PSA > 100 ng/ml; however PSA cutoff to be discussed
- Anti-cancer therapies that are delivered by a filled out-patient prescription

9.3.2 For patients in the VTE sub-population:

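### Recurrent VTE has no event-free interval, so a later coded contact for the same clot can count as a recurrence; to a lesser extent, an old clot can count as a first VTE

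*Protocol*

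**What the plan says.** **Source of events.** Section 9.5 states: "We are also able to use the in- and outpatients registries to detect any diagnosis of VTE events experienced by the patients". The same section shows that the patient registry covers hospital outpatient clinics as well as admissions. The Annex 3 definition is "Venous thromboembolism (composite) I26, I801-802". It has no condition on diagnosis position, type of contact or confirming treatment.

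**Recurrence.** Section 9.8 states: "Time at risk for Objectives 5, 6 and 7 (recurrent VTE, bleeding leading to hospitalisation or death) will be calculated from first cancer-related VTE". Follow-up then runs to the event, death or end of follow-up. Section 9.4.1 adds that only the first event of each type is used. Nothing in the protocol says how a recurrence is told apart from continued care of the index clot.

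**First VTE.** For men with prostate cancer, Section 9.2.3 states "No exclusions will be made". For cancer-free men the only rule under exclusions is "A PC free men diagnosed with a prostate cancer during the follow up will be identified and censored". Section 9.3 lists "previous VTE events" among the baseline characteristics, and Section 9.8 makes no further use of them. Person-time for men with prostate cancer starts at diagnosis. For cancer-free men a first recorded VTE is sought from the date of selection.

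**Checklist (Annex 2).** Items 6.2 (outcomes defined) and 6.3 (outcome validity addressed) are ticked Yes with references to Section 9.3. Item 10.6 (analytic control of outcome misclassification) is ticked No.

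**The concern.** A registry code records a contact, not a new clot. Every man in the VTE subgroup has a recent clot under care, so further contacts carrying the same code are to be expected. These may be a transfer between wards or hospitals, a readmission, a clinic visit, or a PE code following a DVT code within one episode. With risk time opening on the day of the index VTE and no interval before a second code may count, the first such contact meets the written conditions for a recurrence. False events of this kind would fall early, so they would raise the rate (Objective 5) and shorten the time to recurrence (Objective 6). Both are primary objectives, and Section 7 names recurrence risk after different anticoagulants as an evidence gap the study should help to fill.

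The same mechanism works more weakly at baseline. A man whose clot preceded his cancer diagnosis, or his selection as a cancer-free man, stays at risk, and a later follow-up code for that clot can be taken as his first VTE (Objectives 2 and 9; Section 9.8 labels the latter Objective 10).

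**Working it through.** **1. The rules read together.**
- Any inpatient or outpatient code in the list may be used (9.5, Annex 3).
- Recurrence time opens at the index VTE (9.8).
- The first event of the type is the one kept (9.4.1). This does not help, because the first repeat code is exactly the one at issue.
- The protocol does contain gap rules: 90 days in 9.4.1 and six months in 9.4.3. Both apply to dispensings.
- The only VTE time-frame mentioned is deferred: "to define the relatedness, different time-frames will be specified and applied". It concerns the link to the cancer, not whether a code marks a new clot.

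**2. The plan's own precision figure (9.6).** Interval: p ± 1.96·√(p(1−p)/n), with n = 98,000. At p = 3%: √(0.03 × 0.97 / 98,000) = 0.000545; × 1.96 = 0.00107. The interval is 2.89% to 3.11%, as tabulated. The computed width is 0.214 points; the stated 0.22 is the difference of the rounded limits. At 1% and 30% the computed widths are 0.125 and 0.574, against 0.12 and 0.58 stated. The table reproduces, but it covers sampling error only.

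**3. Recurrence: illustration, all inputs assumed.** Let r be the true recurrence risk and f the share of men with a later code for the index clot, taken as independent of true recurrence. Observed = r + (1−r)·f.

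| f | r = 5% | r = 10% |
|---|---|---|
| 5% | 9.75% | 14.5% |
| 10% | 14.5% | 19.0% |
| 30% | 33.5% | 37.0% |
| 50% | 52.5% | 55.0% |

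For example, 0.05 + 0.95 × 0.10 = 0.145. False events outnumber true ones only when f exceeds r/(1−r); at r = 5% this is 0.05/0.95 = 5.3%. At f = 0 there is no bias. The documents do not say where f lies.

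**4. First VTE: illustration, all inputs assumed.** Let t be the true incidence, h the share of men with an earlier VTE, and g the share of those men whose old clot is coded again after baseline. Observed = t(1−h) + h·g + h(1−g)·t = t + h·g·(1−t).
- t = 3%, h = 1%, g = 10%: 0.03 + 0.001 × 0.97 = 3.10% (1.03 times true).
- t = 3%, h = 4%, g = 50%: 0.03 + 0.02 × 0.97 = 4.94% (1.65 times true).

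The excess is 0.10 to 1.94 points, against a half-width of 0.107 points at 3%. At the smallest corner it is just under the half-width; over most of the assumed range it is larger. The effect is weaker than for recurrence because only the share h is exposed to it, whereas every man in the recurrence analysis is.

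**The case against.** Diagnosis position, visit type, look-back and recurrence gap are often left to an analysis plan, and one may exist that settles them. Section 9.5 describes what the data source can do and speaks of events, so it does not say that each coded contact is a new event. The no-exclusion rule governs entry to the cohort. The index event must be cancer-related, earlier VTE is recorded at baseline, and Kaplan-Meier curves by strata are planned, so the groups could be separated. Objectives 2 and 9 ask for the occurrence of VTE, not for first-ever VTE, and a man with an old clot can have a genuine new one.

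Much of this stands as a limit on the claim. The right wording is that such contacts can count, not that they will. Removing men with earlier VTE from the headline rate would be a preference; showing them separately is enough. It does not remove the point, because the protocol goes beyond silence. It fixes an unrestricted source, no exclusions, and a recurrence clock that opens on the index day. It sets gap rules for dispensings but none for VTE. A time-frame for cancer-relatedness would not by itself separate a new clot from a follow-up visit that falls inside it.

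**Conclusion.** The point holds in this form. Under the rules as written, a later coded contact for the index clot can be counted as a recurrence, biasing Objective 5 upward and Objective 6 downward. To a lesser extent, a code for a clot that preceded baseline can be counted as a first VTE in Objectives 2 and 9. The direction follows from the rules. The size does not, because the documents give no rate of repeat coding, true recurrence or earlier VTE. The figures in the working only show how the bias depends on those unknowns.

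A reader might go further in two ways that the documents do not support. One is that Objectives 5 and 6 would mainly measure clinic scheduling. That requires repeat coding above about 5% when true recurrence is 5%, and neither figure is known. The other is that the error differs between treatment types or durations because men treated for longer have more visits. This is plausible, but nothing in the protocol shows it.

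**What to change.** **(a) Recurrence.**
- Count a recurrence only when a VTE code falls after a fixed interval from the index VTE date, for example 90 days. Apply the interval to inpatient and outpatient codes alike.
- Merge transfers and contiguous stays into one episode.
- Start recurrence time at risk at the end of the interval.
- Repeat with 30- and 180-day intervals, and with inpatient main-diagnosis events only.

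Measuring the interval from the index date, not from the latest coded contact, keeps frequent clinic visits from resetting it.

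**(b) First VTE.** Using the earlier-VTE variable already planned, report the Objective 2 and 9 rates separately for men with and without a VTE code in a fixed look-back before baseline. Use the same look-back in both cohorts.

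**Cost.** The change needs wording and programming, and no new data. True recurrences inside the interval are missed, and men who die or are censored within it drop out of the recurrence analysis. With a 90-day interval, men treated for up to 3 months would contribute little or no on-treatment risk time, so that stratum has to be read mainly from the 30-day analysis. The sensitivity analyses show how far the result depends on these choices.
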